#### **2.2 Secondary Objectives**

- 2.2.1 To determine the correlation between ASL-measured baseline perfusion and the treatment response (PFS, OS).
- 2.2.2 To determine the correlation between post-treatment changes in ASL-measured perfusion at T1, T2 and T3 compared to baseline and the treatment response (PFS, OS).
- 2.2.3. To predict responders from non-responders (progression versus not at 7 months) with measurements at baseline and at earlier time points (T1 and T2) using:
  - a. ASL-measured perfusion alone
  - b. ASL-measured perfusion in combination with other MR imaging metrics such as diffusion weighted imaging (DWI) derived apparent diffusion coefficient (ADC), and chemical exchange saturation transfer (CEST) measured CEST effect.

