**10.2 Sample Size and Accrual**

The sample size is calculated based on the primary objective. A significant correlation of 0.75 was observed between one month ASL perfusion change and time to progression in our RCC patients, whereas the corresponding tumor size change was not correlated with time to progression (19). We expect approximately 50% of RCC patients to progress within 7 months of imaging protocol. Beyond this time point, patients will be followed according to their clinical scans for the next 3 years or until death. Using such information, we target 40 subjects for this study and anticipate approximately 20 subjects to progress within the 7 months period. This sample size would provide more than 95% power to detect a correlation of 0.75 between earlier perfusion changes (at T2 and T6) and time to progression, using two-sided correlation test at a significance level of 0.05.

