**10.3 Data Analyses Plans**

The perfusion difference images and the absolute quantified images will be converted to DICOM and transferred to a DICOM database (e.g. iPACS, OsiriX). A semi-automated segmentation algorithm and region of interest (ROI) based measures will be performed to extract perfusion measures. Percentage changes in perfusion within each ROI will be calculated at each follow-up MRI compared to the baseline image. The semi-automated tumor ROIs will be compared to expert segmentation by [name] in all cases, who will also supervise the trainee (to be recruited) in the analysis. Additionally, morphological changes will also be calculated according to RECIST and 10% reduction in the sum of the largest diameters (20).

Among patients with disease progression, one-sample correlation test will be used to determine the correlation between change in ASL measured tumor perfusion during and immediately after treatment and time to progression, and the correlation between change in ASL measured tumor perfusion during and immediately after treatment and the corresponding tumor size change. The correlations will be measured and compared using Pearson's correlation coefficient along with 95% confidence interval. PFS and OS will be correlated with baseline perfusion and post-treatment changes at T1 and T2

compared to baseline using univariable and multivariable Cox regression models. We used PFS at 7 months as a cutoff point to divide patients into “responders” versus “non-responders” in this study. Univariable and multivariable logistic regression models will be used to predict responders from non-responders with ASL measurements at baseline and at earlier time points (T1 and T2) alone, and in combination with other MR imaging metrics. The statistical analysis will also be performed separately for male and female subjects to evaluate sex as a biological variable.

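### The logistic prediction models for objective 2.2.3 rest on about 20 events with no term limit, shrinkage or internal validation, so their performance will be overstated and the combined model will usually look better than it is

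*Combined protocol and SAP*

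**What the plan says.** Section 2.2 (objective 2.2.3) sets out to separate responders from non-responders, defined by progression status at 7 months, using measurements at baseline, T1 and T2. It lists two predictor sets. Set (a) is ASL perfusion alone. Set (b) is "ASL-measured perfusion in combination with other MR imaging metrics such as diffusion weighted imaging (DWI) derived apparent diffusion coefficient (ADC"), with the CEST effect named next. The list in (b) is open-ended.

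Section 10.3 supplies the method: "Univariable and multivariable logistic regression models will be used to predict responders from non-responders", with ASL measurements at the three early time points alone and combined with the other metrics. The same section repeats the statistical analysis in men and women separately.

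Section 10.2 gives the numbers: "we target 40 subjects for this study and anticipate approximately 20 subjects to progress within the 7 months period". It also states that "The sample size is calculated based on the primary objective", so objective 2.2.3 is not sized.

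The Study Schema makes attendance at both T1 and T2 optional.

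No section states how many terms enter a model, how they are selected or how performance is measured. None mentions penalisation, cross-validation, bootstrap correction or a separate validation set.

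**The concern.** The stated aim is prediction, so what matters is how well the models classify patients who were not used to fit them. The plan has no means of estimating that. Maximum-likelihood logistic regression with few events per term fits chance patterns, and any performance figure from the same patients includes them.

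The two predictor sets make this worse. Set (b) contains set (a), so the fitted likelihood of (b) can never be lower, and its apparent discrimination is rarely lower. A reader shown both results will compare them. At stake is a published impression that ADC and CEST add predictive value to ASL when they may add nothing, or may worsen prediction in new patients.

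**Working it through.** **Inputs from the documents.** 40 RCC patients; "We expect approximately 50% of RCC patients to progress within 7 months of imaging protocol"; predictors at baseline, T1 and T2; metrics ASL, ADC and CEST; unpenalised logistic regression.

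**The plan's own figures.** Events: 40 × 0.50 = 20, leaving 20 non-progressors. The only power statement is "This sample size would provide more than 95% power to detect a correlation of 0.75", "using two-sided correlation test at a significance level of 0.05". With n = 20 progressors, Fisher's z gives Φ(atanh(0.75) × √17 − 1.960) = Φ(0.973 × 4.123 − 1.960) = Φ(2.05) = 0.980. A simulation of the t-test for Pearson's r gives 0.983. The figure reproduces, but it concerns the primary correlation and says nothing about objective 2.2.3.

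**Assumed inputs.** The number of terms is not stated. I took one, two or three time points per metric. ASL alone then has 1, 2 or 3 terms, and ASL + ADC + CEST has 3, 6 or 9. Events per term in the combined model are 20/3 = 6.7, 20/6 = 3.3 and 20/9 = 2.2.

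**Simulation.** 20 progressors and 20 non-progressors; independent normal predictors; 600 datasets per setting. The first ASL term is shifted by d SD between the groups and every other term is noise. Apparent AUC is computed on the 40 fitted patients, and new-patient AUC on 2,000 fresh patients per dataset. The last column is a 5% likelihood-ratio (LR) test of the terms that (b) adds to (a).

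| d | Terms (a) vs (b) | Apparent AUC (a) → (b) | New-patient AUC (a) → (b) | (b) has higher apparent AUC | LR test accepts noise terms |
|---|---|---|---|---|---|
| 0.8 | 1 vs 3 | 0.708 → 0.746 | 0.711 → 0.676 | 86% | 8% |
| 0.8 | 2 vs 6 | 0.739 → 0.798 | 0.695 → 0.652 | 96% | 8% |
| 0.8 | 3 vs 9 | 0.748 → 0.835 | 0.679 → 0.627 | 99% | 14% |
| 0 | 1 vs 3 | 0.572 → 0.647 | 0.500 → 0.501 | 92% | 6% |
| 0 | 2 vs 6 | 0.610 → 0.715 | 0.499 → 0.499 | 98% | 8% |
| 0 | 3 vs 9 | 0.644 → 0.771 | 0.500 → 0.500 | 100% | 14% |

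Repeat runs moved these AUC means by about 0.02 at most. With d = 1.2 the pattern is the same: (b) has the higher apparent AUC in 85%, 95% and 99% of runs, and the LR test accepts noise in 7%, 11% and 15%.

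**Optimism of the combined model at d = 0.8** (apparent minus new-patient AUC): 0.746 − 0.676 = 0.070 with 3 terms, 0.798 − 0.652 = 0.146 with 6, and 0.835 − 0.627 = 0.208 with 9.

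**Does bootstrap correction alone cure it?** At d = 0.8 with 1 versus 3 terms, yes: corrected AUC is 0.71 for (a) and 0.69 for (b), the right order. With 3 versus 9 terms, no: corrected AUC is 0.69 for (a) and 0.69 to 0.71 for (b), against 0.68 and about 0.63 in new patients. With pure noise and 3 versus 9 terms, the corrected values (0.55 and 0.59) still favour (b).

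**Smaller samples.** If optional T1/T2 attendance left 30 complete cases with 15 events (an assumption), 3 versus 9 terms at d = 0.8 gives apparent AUC 0.766 → 0.879 and new-patient AUC 0.669 → 0.609. In a sex subgroup of 20 patients with 10 events (an even split, assumed), a 9-term model gives apparent AUC 0.92 to 0.97 over d = 0 to 1.2. It separates the groups perfectly in 40% to 75% of runs, so finite maximum-likelihood estimates do not exist. With 3 terms, separation occurs in at most 4% of runs.

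**The case against.** Objective 2.2.3 lists (a) and (b) as two predictor sets. Neither it nor section 10.3 says that they will be compared, that one will be preferred, or that added value will be claimed. AUC appears nowhere in the documents. If the added terms were judged by an ordinary likelihood-ratio test, noise would be accepted in only about 6% to 15% of runs. Nine terms is an assumed worst case, and optional attendance at T1 and T2 makes a model using all three visits less likely. With three terms the shift is modest. The objective is secondary, and treatment is left to the referring physician (section 4.4).

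All of this stands, and it limits the point. A reader might infer that the plan commits the team to a contest that the combined model is bound to win. The documents do not support that. Only the likelihood is certain not to fall, and a higher apparent AUC is usual (about 85% to 100% of runs), not guaranteed. A reader might also take nine terms as planned, but no term count is given.

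The objection does not remove the gap. The aim is prediction, the method is unpenalised fitting, and nothing in the plan estimates performance in new patients. The direction of the error is the same from 3 to 9 terms.

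**Conclusion.** The point holds as a gap in specification with a predictable direction of error. With about 20 progressors among 40 patients and no term limit, shrinkage or internal validation, performance judged on the same patients will be optimistic. If the added metrics are noise, the combined model will usually look better than ASL alone while predicting new patients less well, or no better when ASL is uninformative too.

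With one informative ASL term, the misleading apparent gain in AUC is about 0.04 (1 versus 3 terms) to 0.09 (3 versus 9). The true loss in new patients is about 0.04 to 0.05. These sizes rest on the assumed term counts, independent normal predictors, a 0.8 SD effect and exactly 20 events.

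A reader might extend this to the study's power or its primary correlation analysis. This point does not touch either, and the stated power reproduces. The change is worth making because it is cheap, but the study does not stand or fall on it.

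**What to change.** Amend section 10.3 as follows.

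1. Cap the multivariable model at about three terms chosen before the data are seen, and fit it by penalised (ridge or Firth) logistic regression. The team decides which baseline, T1 or T2 measures of ASL, ADC and CEST to use. This step comes first, because bootstrap correction without the cap is not enough.
2. Report bootstrap optimism-corrected AUC and calibration for (a) and (b), repeating the whole modelling process in each resample. Give the corrected difference with a confidence interval, and label any conclusion about added value exploratory.
3. Do not refit the multivariable prediction models separately by sex.

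The cost is a little more analysis time, lower reported AUCs, and giving up a single model that holds every metric at every time point. No extra patients, scans or visits are needed, and the primary analysis is unchanged.

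### Section 10.3 evaluates sex only by repeating the analyses in men and in women, with no planned between-sex comparison, so a sex difference is neither estimated nor tested

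*Combined protocol and SAP*

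**What the plan says.** The last sentence of section 10.3 is the only statement on sex as an analysis variable: "The statistical analysis will also be performed separately for male and female subjects to evaluate sex as a biological variable". It follows the correlation, Cox and logistic analyses and is not limited to any one of them, so it is fairly read as covering all three.

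The correlation analysis is restricted to progressors: "Among patients with disease progression, one-sample correlation test will be used". Section 10.3 adds: "The correlations will be measured and compared using Pearson's correlation coefficient along with 95% confidence interval". The correlations named there are perfusion change with time to progression and perfusion change with tumor size change. Men versus women is not among them.

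Section 10.2 sizes the study for one overall correlation: "we target 40 subjects for this study and anticipate approximately 20 subjects to progress within the 7 months period", giving "more than 95% power to detect a correlation of 0.75", "using two-sided correlation test at a significance level of 0.05". It gives no expected sex split and no power by sex. Sex does not appear in the objectives (sections 2.1 to 2.3), the endpoints (2.4) or the hypothesis (10.1). The sex analysis is not labelled exploratory.

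**The concern.** Whether sex modifies the link between perfusion change and outcome is a question about a difference between two associations. A one-sample test of zero correlation in men and another in women answer two other questions. Neither gives an estimate, an interval or a p-value for the difference.

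The practical risk lies in how such output is read. With small groups, one sex can reach significance and the other miss it when the underlying association is the same. A reader given only the two results may conclude that ASL perfusion is informative in one sex and not the other. The plan supplies nothing that would correct that reading.

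**Working it through.** **Inputs.** From section 10.2: correlation 0.75, about 20 progressors, two-sided alpha 0.05, 40 RCC patients. From section 10.3: the correlation is tested among progressors. Assumed: the sex split of the progressors, shown as a range, and bivariate normal data.

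**Step 1: the plan's own power.** By Fisher z, power = Φ(√(n−3) × atanh(ρ) − 1.96). With n = 20 and ρ = 0.75: √17 × 0.973 − 1.96 = 4.012 − 1.96 = 2.05, and Φ(2.05) = 98.0%. Simulation of the Pearson test (200,000 runs) gives 98.4%. Both agree with the stated figure of more than 95%.

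**Step 2: one sex significant, the other not, when the sexes do not differ.** Let p1 and p2 be the power in the larger and smaller group. The chance that exactly one is significant is p1(1−p2) + p2(1−p1). Simulated power at ρ = 0.75 in both sexes gives:

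| Split | p1 | p2 | Exactly one significant |
|---|---|---|---|
| 10/10 | 0.778 | 0.777 | 35% |
| 12/8 | 0.864 | 0.646 | 39% |
| 13/7 | 0.894 | 0.561 | 45% |
| 14/6 | 0.919 | 0.454 | 54% |
| 15/5 | 0.937 | 0.331 | 65% |

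For 13/7, for example: 0.894 × 0.439 + 0.561 × 0.106 = 0.392 + 0.059 = 0.45.

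**Step 3: other assumptions.**
- True correlation 0.5 in both sexes, 20 progressors: 44% (10/10) to 50% (15/5).
- No correlation in either sex: 2 × 0.05 × 0.95 = 9.5%.
- All 40 patients progress, ρ = 0.75: at 20/20, 2 × 0.984 × 0.016 = 3%. At 28/12, power in the larger group is close to 1, so the chance is about 1 − 0.864 = 14%.
- All 40 progress, ρ = 0.5: at 20/20, 2 × 0.641 × 0.359 = 46%.

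**Step 4: a direct comparison.** Test atanh(r_men) − atanh(r_women) with SE = √(1/(n1−3) + 1/(n2−3)). With ρ = 0.75 in both sexes, its simulated type I error is 4.3% to 4.7% for splits from 10/10 to 15/5. Its power for 0.75 in one sex against 0 in the other is:
- 10/10: SE = √(2/7) = 0.535; 0.973/0.535 = 1.82; Φ(1.82 − 1.96) = 44%.
- 14/6: SE = √(1/11 + 1/3) = 0.651; 0.973/0.651 = 1.49; power 32%.
- 15/5: SE = √(1/12 + 1/2) = 0.764; 0.973/0.764 = 1.27; power 25%.

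For 0.75 against 0.5, power is 12%, 10% and 9% for the same splits.

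No corresponding calculation was made for the Cox and logistic models, which are not restricted to progressors.

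**The case against.** Several points on the other side have force.

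- **The plan states no faulty inference rule.** A reader might infer that the sponsor intends to set a significant result in one sex against a non-significant one in the other. Section 10.3 does not say so. It plans 95% CIs for the correlations, so repeating that analysis by sex gives estimates with intervals. Discordant p-values are not the same as a reported sex difference. This stands, but two separate intervals are not an interval for the difference. An observed correlation of 0.75 has a 95% CI of 0.23 to 0.94 at n = 10 and −0.16 to 0.97 at n = 6.
- **Separate analyses do not make a comparison impossible.** Two independent correlations can be compared afterwards by Fisher z. The supportable statement is that no comparison is pre-specified, not that none could be made.
- **The smaller group need not miss significance.** It is tempting to say that the smaller sex group will usually be non-significant. At 13/7 its power is 56%, and at 12/8 it is 65%. It is more likely than not to miss only with 6 or fewer progressors, and the documents give no split.
- **Twenty progressors is a 7-month figure.** Section 10.2 continues: "Beyond this time point, patients will be followed according to their clinical scans for the next 3 years or until death". Section 10.3 sets no 7-month limit on the progressors analysed, so the number could rise, and at ρ = 0.75 the problem then largely recedes. It does not recede at ρ = 0.5. The number could also be below 20, because objective 2.1.1 covers anti-angiogenic patients only while criterion 3.1.2 also admits immunotherapy patients.
- **The sex analysis carries no primary or secondary conclusion.** This stands, and it limits the importance of the point.

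**Conclusion.** The point holds as a minor one. Separate analysis is the only method that section 10.3 gives for evaluating sex, and it neither estimates nor tests a sex difference. With about 20 progressors and the plan's correlation of 0.75 in both sexes, the chance of a significant result in exactly one sex is about 35% (10/10), 45% (13/7) or 54% (14/6). These figures concern the progressor correlation only and rest on an assumed split and equal true correlations. They fall to 3% (20/20) or 14% (28/12) with 40 progressors at ρ = 0.75, but remain about 46% (20/20) at ρ = 0.5.

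A reader might go further and infer that a direct comparison would settle the sex question. It would not: with 20 progressors its power is only about 25% to 44% even for 0.75 against 0. It corrects the inference but cannot supply the information.

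**What to change.** Replace the last sentence of section 10.3 with text to this effect:

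- For the correlations, the male-female difference will be estimated on the Fisher z scale and reported with its 95% CI.
- For the Cox and logistic models, sex and a sex-by-perfusion-change term will be added to the pooled model, and the interaction estimate will be reported with its 95% CI.
- Sex-specific estimates with 95% CIs will be reported descriptively, without separate significance tests.
- The sex analysis is exploratory.

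The correlations need their own method because a Pearson correlation has no pooled model to take an interaction term, and an interaction in a linear model would compare slopes rather than correlations.

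The cost is a few sentences and little extra analysis, with no change to sample size, visits or data collection. The downside is that the between-sex comparison will be imprecise, so the report should say that a wide interval including no difference does not rule out a sex difference.

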## **11.0 STUDY MANAGEMENT**

### **11.1 Conflict of Interest**

Any investigator who has a conflict of interest with this study (patent ownership, royalties, or financial gain greater than the minimum allowable by their institution, etc.) must have the conflict reviewed by the UTSW COI Committee and IRB according to UTSW Policy on Conflicts of Interest. All investigators will follow the University conflict of interest policy.

### **11.2 Institutional Review Board (IRB) Approval and Consent**

It is expected that the IRB will have the proper representation and function in accordance with federally mandated regulations. The IRB must approve the consent form and protocol.

In obtaining and documenting informed consent, the investigator should comply with the applicable regulatory requirement(s), and should adhere to Good Clinical Practice (GCP) and to ethical principles that have their origin in the Declaration of Helsinki.

Before recruitment and enrollment onto this study, the subject will be given a full explanation of the study and will be given the opportunity to review the consent form. Each consent form must include all the relevant elements currently required by the FDA Regulations and local or state regulations. Once this essential information has been provided to the subject and the investigator is assured that the subject understands the implications of participating in the study, the subject will be asked to give consent to participate in the study by signing an IRB-approved consent form.

Prior to a patient's participation in the trial, the written informed consent form should be signed and personally dated by the subject or legally authorized representative and by the person who conducted the informed consent discussion.

### **11.3 Registration Procedures**

All subjects must be registered with the Radiology Clinical Trials Office before enrollment to study. Prior to registration, eligibility criteria must be confirmed with the Radiology Clinical Trials Office Study Coordinator. To register a subject, call [contact] Monday through Friday, 9:00AM-5:00PM.

New subjects will receive a number beginning with 001 upon study consent such that the first subject consented is numbered 001, the second subject consented receives the number 002, etc.

Each newly consented subject should be numbered using the schema provided above. Upon registration, the registrar will assign the additional registration code according to the numbering schema outlined above, which should then be entered as the patient study id in Velos upon updating the status to be enrolled.

The numbering schema should clearly identify the site number; the sequential number of the subject enrolled as well as the status of the subjects enrolled so that the number of subjects consented versus the number of subjects actually enrolled may be easily identified.

**11.4 Data Management and Monitoring/Auditing**

REDCap is the UTSW SCCC institutional choice for the electronic data capture of case report forms for this and all SCCC Investigator Initiated Trials. REDCap will be used for electronic case report forms in accordance with Simmons Comprehensive Cancer Center requirements.

Trial monitoring will be conducted no less than annually and refers to a regular interval review of trial related activity and documentation performed by the DOT, which includes but is not limited to accuracy of case report forms, protocol compliance, timeliness and accuracy of Velos entries and AE/SAE management and reporting. Documentation of trial monitoring will be maintained along with other protocol related documents and will be reviewed during internal audit.

The UTSW Simmons Comprehensive Cancer Center (SCCC) Data Safety Monitoring Committee (DSMC) is responsible for monitoring data quality and patient safety for all UTSW SCCC clinical trials. As part of that responsibility, the DSMC reviews all local serious adverse events and UPIRSOs in real time as they are reported and reviews adverse events on a quarterly basis. The quality assurance activity for the Clinical Research Office provides for periodic auditing of clinical research documents to ensure data integrity and regulatory compliance. A copy of the DSMC plan is available upon request.

The SCCC DSMC meets quarterly and conducts annual comprehensive reviews of ongoing clinical trials, for which it serves as the DSMC of record. The QAC works as part of the DSMC to conduct regular audits based on the level of risk. Audit findings are reviewed at the next available DSMC meeting. In this way, frequency of DSMC monitoring is dependent upon the level of risk. Risk level is determined by the DSMC Chairman and a number of factors such as the phase of the study; the type of investigational agent, device or intervention being studied; and monitoring required to ensure the safety of study subjects based on the associated risks of the study. Protocol-specific DSMC plans must be consistent with these principles.

